5 SELECTION AND WITHDRAWAL OF SUBJECTS

5.1 Inclusion Criteria

A subject must meet all the following inclusion criteria to be eligible for participation in this study:

1. Hospitalized male or female subjects of ≥ 18 years of age at time of Screening who are being treated in the ICU for COVID-19 for not longer than 48 hours or for whom a decision has been made that COVID-19 disease severity warrants ICU admission.
2. Has laboratory-confirmed novel coronavirus (SARS-CoV-2) infection as determined by qualitative PCR (reverse transcriptase [RT]-PCR), or other FDA-approved-or regulatory-

GRIFOLS Bioscience Industrial Group	Number	BLG-CL-PRT-000020	Version	4.0	Status	Effective	Effective Date	19-Jul-2021	41 of 91
	GC2007 - A Multicenter, Randomized, Open-label Parallel Group Pilot Study to Evaluate Safety and Efficacy of High Dose Intravenous Immune Globulin (IVIG) plus Standard Medical Treatment (SMT) versus SMT alone in						Page		

authority-approved diagnostic assay for COVID-19 in any specimen during the current hospital admission prior to randomization.

3. Illness (symptoms of COVID-19 of any duration requiring ICU level care), and the following:
 - a) Radiographic infiltrates by imaging (chest X-Ray, CT scan, etc.), AND
 - b) Requiring mechanical ventilation and/or supplemental oxygen.

Note: ICU level care is defined as the medical need for intensive or invasive monitoring; immediate or impending need for supportive care of the airway, breathing, or circulation; and/or stabilization of acute severe or life-threatening complications of COVID-19.
4. Any one of the following related to COVID-19: i. Ferritin > 400ng/mL, ii. LDH > 300 U/L, iii. D-Dimers > reference range, or iv. C-reactive protein (CRP) > 40 mg/L.
5. Subject provides informed consent prior to initiation of any study procedures.

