
 Record clinical features key symptoms: fever, cough, shortness of breath, fatigue, myalgia etc. Vital signs (temperature, systolic and diastolic blood pressure, pulse, respiratory rate) Initial Body Weight (this weight is to be used to calculate all IVIG doses if randomized to combination arm with Gamunex-C) Record result of historical SARS-CoV-2 PCR (qualitative RT-PCR) or other FDA-approved or regulatory-authority-approved diagnostic assay in any specimen during the current hospital admission prior to randomization (eligibility criterion) Record hospital admission date Record ICU admission date Record supplemental oxygen administration (type, %, flow start/end date/time) Record details of mechanical ventilation parameters (start/end date/time) Record oxygen saturation (specify on or off oxygen supplementation) Assessment of ARDS (Berlin Criteria) (Appendix 3) SOFA score (Appendix 4) Respiratory sample for quantitative measurement of SARS-CoV-2 viral load by NAT or PCR (real-time RT-PCR) (obtained via nasopharyngeal swab) Sample for quantitative measurement of IgM and IgG antibodies to SARS-CoV-2 by enzyme linked immunosorbent assay (ELISA), Indirect Fluorescent Antibody (IFA), or another assay methodology (store serum samples frozen at -70°C for later analysis at an external lab) Serum Chemistry (creatinine, albumin, alanine aminotransferase [ALT], total bilirubin, lactate dehydrogenase [LDH]) Hematology: absolute lymphocyte count and standard hematology (hemoglobin, hematocrit, platelet count, leukocyte count with differential) Ferritin (serum), D-dimer (plasma, sodium citrate tube), CRP (serum) Direct antiglobulin test (DAT) Cytokine panel (IL-1β, IL-10, IL-6, IL-8, IL-2, interferon γ, and TNF-α). Note: serum samples must be stored at -70°C for later analysis at a reference laboratory. Record daily 24-hour fluid balance (intake and output) Record body weight a second time for assessing fluid balance on Day 1 (at least 8 hours should separate the time from the first recorded weight) Record SAEs and TEAEs Record standard care concomitant medications 									

GRIFOLS Bioscience Industrial Group	Number	BLG-CL-PRT-000020	Version	4.0	Status	Effective	Effective Date	19-Jul-2021	50 of 91
	GC2007 - A Multicenter, Randomized, Open-label Parallel Group Pilot Study to Evaluate Safety and Efficacy of High Dose Intravenous Immune Globulin (IVIG) plus Standard Medical Treatment (SMT) versus SMT alone in								

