### 2.2.2 Secondary Efficacy Endpoints

The secondary efficacy endpoints include the following:

- Time to actual ICU discharge: defined as duration of ICU stay from Day 1 through Day 29
  - Additionally, time to a medical equivalence of ICU discharge will be recorded and analyzed (defined as the time point when the patient no longer requires ICU level care, ie, not requiring invasive mechanical ventilation, or intensive monitoring such as arterial line or central line placement, administration of IV vasopressors to support blood pressure, or O2 supplementation greater than that delivered by nasal cannula)
- Duration of mechanical ventilation from Day 1 through Day 29
- Time to actual hospital discharge: defined as duration of hospitalization from Day 1 through Day 29
  - Additionally, time to a medical equivalence of hospital discharge will be recorded and analyzed (defined as the time point when the patient no longer requires supplemental oxygen and no longer requires ongoing medical care [yet may not be discharged from hospital for social or quarantine reasons])
- Duration of any oxygen use Day 1 through Day 29
- Absolute value and mean change from baseline in the Ordinal scale Day 1 through Day 29

The Ordinal scale is as follows:

- 1) Death;
- 2) Hospitalized, on invasive mechanical ventilation or extracorporeal membrane oxygenation (ECMO);
- 3) Hospitalized, on non-invasive ventilation or high flow oxygen devices;
- 4) Hospitalized, requiring supplemental oxygen;
- 5) Hospitalized, not requiring supplemental oxygen;
- 6) Not hospitalized, limitation on activities;
- 7) Not hospitalized, no limitations on activities.

- Proportion (percentage) of subjects in each severity category of the 7-point Ordinal scale at Day 15 and Day 29
- Number of subjects who develop Acute Respiratory Distress Syndrome (ARDS) overall and distribution by severity through Day 29
- Change from baseline in SOFA score at Day 5, Day 15, and Day 29

- Assessment of Clinical Severity: Change in NEWS from baseline (Day 1 through Day 29).  
The NEWS has demonstrated an ability to discriminate patients at risk of poor outcomes. This score is based on 7 clinical parameters (respiration rate, oxygen saturation, any supplemental oxygen, temperature, systolic blood pressure, heart rate, level of consciousness [Alert, Voice, Pain, Unresponsive]).
- Time to clinical response: NEWS  $\leq 2$  maintained for 24 hours, Day 1 through Day 29

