#### 4.6 Data Derivations and Transformations

The following derivations will be used in this study:

Study Day:

- Date of assessment – date of randomization + 1 for assessments done on or after date of randomization
- Date of assessment – date of randomization for assessments done before date of randomization

Baseline Observation: the last non-missing value prior to randomization.

Duration:

- Duration in days = end date – start date + 1
- Duration in minutes = end time in minutes – start time in minutes

Origin or Start Date for Time to Event Endpoints:

- Time to death: date of randomization
- Time to ICU Discharge (actual and medical equivalence, if applicable): date of randomization or date of ICU admission, whichever was later
- Time to Hospital Discharge (actual and medical equivalence, if applicable): date of randomization
- Time to Clinical Response: date of randomization

Event Date for Time to Clinical Response:

- If a subject met the criteria for clinical response at multiple assessments, the date of the first assessment meeting the definition of clinical response will be used as the event date for deriving time to clinical response.

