## 6. EFFICACY ANALYSES

All efficacy analyses will be carried out using the ITT population. Data on all efficacy endpoints will be listed and tabulated if appropriate.

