### **Number of subjects developed ARDS**

Berlin criteria for ARDS will be assessed on Days 1, 5, 15, and 29. The presence of ARDS and the degree of ARDS by Berlin criteria (Mild, Moderate, Severe) will be tabulated by treatment group at each visit.

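### The ARDS endpoint counts subjects who develop ARDS through Day 29, but the SAP plans only by-visit tables, which cannot yield that count and have no stated denominator or rule for deaths

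*SAP*

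**What the plan says.** SAP 2.2.2, in the same words as protocol 4.1.2, lists this secondary efficacy endpoint: "Number of subjects who develop Acute Respiratory Distress Syndrome (ARDS) overall and distribution by severity through Day 29".

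SAP 6.2, under Number of subjects developed ARDS, gives the whole analysis in two sentences. The first sets the times: "Berlin criteria for ARDS will be assessed on Days 1, 5, 15, and 29". The second sets the summary: "The presence of ARDS and the degree of ARDS by Berlin criteria (Mild, Moderate, Severe) will be tabulated by treatment group at each visit".

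Other text that bears on it:

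- SAP 6: "All efficacy analyses will be carried out using the ITT population". It adds: "Data on all efficacy endpoints will be listed and tabulated if appropriate".
- SAP 4.6: "Baseline Observation: the last non-missing value prior to randomization". The ARDS paragraph does not use this definition.
- SAP 4.4 promises worst-case imputation, where applicable, for missing binary efficacy data and sends the reader to Section 6 for details. The ARDS paragraph has none.
- Protocol 5.1 requires radiographic infiltrates and, as a further condition, "Requiring mechanical ventilation and/or supplemental oxygen". Protocol 5.2 does not exclude ARDS at entry, and protocol 7.2.2 schedules a Berlin assessment at baseline.

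**The concern.** The endpoint follows each subject over time and counts that subject once. The planned summary is four cross-sections. A subject with ARDS on Days 1, 5 and 15 appears in three of them, and a subject who already had ARDS on Day 1 is mixed with one who acquired it by Day 5. Carrying out the SAP exactly as written would therefore leave a listed secondary endpoint without an estimate.

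Two consequences follow. First, whoever produces the count later must choose the numerator, the denominator and the treatment of deaths, in an open-label trial and possibly with the data in view. Second, if the by-visit tables are read as the answer, baseline cases dilute any difference in new ARDS. At later visits, deaths among ARDS cases can shrink the difference or change its direction, depending on a denominator that the plan does not state.

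**Working it through.** The documents give no ARDS rate, effect size or ARDS-based sample size, so there is no planned figure to reproduce. The check compares the texts, then asks what the planned table can determine. All ARDS and death counts below are assumptions. The 50 per arm comes from about 100 subjects randomized 1:1 (SAP 3.1 and 9).

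**Texts side by side.** Where the SAP wants a visit-specific endpoint, it names the visits: ordinal categories at Days 15 and 29, and hyperinflammation on Days 1, 5, 15 and 29. The ARDS endpoint instead runs through Day 29. No other section supplies a per-subject ARDS count. Protocol 9.1 names methods for time-to-event and continuous secondary variables, but none for this count.

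**What by-visit totals determine.** Let x1 be the Day 1 count, xv the count at visit v (Days 5, 15, 29), and n = 50.

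- New-onset minimum = largest of max(0, xv − x1); maximum = min(n − x1, sum of xv).
- Ever-ARDS minimum = largest visit count; maximum = min(n, sum of all four counts).

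| Assumed counts, Days 1/5/15/29 | Free on Day 1 | New-onset range | Ever-ARDS range |
|---|---|---|---|
| 10/10/6/3 | 40 | 0 to 19 (0% to 48%) | 10 to 29 |
| 25/20/12/5 | 25 | 0 to 25 (0% to 100%) | 25 to 50 |
| 35/28/15/6 | 15 | 0 to 15 (0% to 100%) | 35 to 50 |

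In the second row, for example, the sum of xv is 20 + 12 + 5 = 37, capped at the 25 subjects at risk. Two arms could both show 25/20/12/5 and yet have 3/25 and 12/25 new cases (12% v 48%, Fisher p = 0.012).

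**Dilution by baseline cases.** Assume 30 of 50 per arm have ARDS on Day 1, and that 8 (SMT) v 4 (IVIG) of the 20 at risk develop it by Day 5.

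- New onset: 8/20 = 40% v 4/20 = 20%, a difference of 20 points.
- Day 5 table, with no resolution and no deaths yet: (30 + 8)/50 = 76% v (30 + 4)/50 = 68%, a difference of 8 points.

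**Denominator at Day 29.** Continue with no resolution and no further new cases, and 15 v 10 deaths, all among ARDS cases.

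| Reading of the table | SMT | IVIG |
|---|---|---|
| Survivors only | (38 − 15)/(50 − 15) = 23/35 = 66% | (34 − 10)/(50 − 10) = 24/40 = 60% |
| All randomized, deaths not counted as ARDS | 23/50 = 46% | 24/50 = 48% |
| All randomized, deaths counted as ARDS | 38/50 = 76% | 34/50 = 68% |

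The same data give three different pictures, and the second reverses the order of the arms. Among survivors, reversal needs a wider mortality gap: with 20 v 8 deaths, the table shows 18/30 = 60% v 26/42 = 62%.

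**The case against.** The best defence is that little depends on this table. ARDS is one of many secondary endpoints in a pilot without multiplicity adjustment, no ARDS test is planned, and the secondary objective does not name ARDS. Day 1 is tabulated, so baseline prevalence will be visible. Subject-level data are collected and listed, so the count can be recovered. Even the corrected comparison is weak: 8/20 v 4/20 gives Fisher p = 0.30. All of this stands and limits the weight of the point. It does not supply the missing estimate, because a listing defines no numerator, denominator or worst-grade rule.

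A reader might infer more than the documents support:

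- *That the Day 15 and Day 29 tables cover only subjects alive and assessed.* SAP 6.2 gives no denominator. SAP 6 specifies ITT and SAP 4.4 mentions worst-case imputation. The survivor-only table is one possible reading.
- *That many subjects will have ARDS on Day 1.* The share is not stated. Entry accepts any supplemental oxygen, whereas all three Berlin grades in protocol Appendix 3 require PEEP or CPAP (with an SpO2/FiO2 substitute allowed off the ventilator).
- *That the endpoint can only mean new onset.* The wording also allows ARDS at any time through Day 29. The by-visit totals give neither count.
- *That deaths will make the worse arm look better.* In the survivor-only example with 15 v 10 deaths they only narrow the gap. Reversal depends on the denominator or on a larger mortality difference.

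**Conclusion.** The mismatch is real: followed as written, the SAP does not estimate its own ARDS endpoint on either reading of the wording. The denominator and the rules for death and missing assessments are unset as well, since SAP 4.4 defers to details that SAP 6.2 does not give for ARDS. Missing assessments are a practical matter, because protocol 4.2 allows Day 15 and Day 29 by phone and its examples of what to collect that way do not include the Berlin criteria.

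The conclusion about the text needs no assumption about rates. That Day 1 cases stay in the later tables is inferred from the ITT population and the absence of any exclusion. The size in this trial cannot be computed. The figures above show what is possible under assumed counts, with no resolution of ARDS in the dilution and Day 29 examples. The gap is in the specified analysis and not in data collection. It should be closed, but it does not touch the primary endpoint.

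**What to change.** Add one table per arm to SAP 6.2:

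- **Main count.** Among subjects without Berlin ARDS at baseline (SAP 4.6 definition), the number and percent meeting the criteria at any post-baseline assessment (Days 5, 15, 29), each counted once at worst severity. Show death before ARDS and no post-baseline assessment as separate categories, and say how a subject with only some assessments is classed. Give the between-arm difference with a 95% CI.
- **Companion display.** Worst post-baseline severity for all ITT subjects, split by baseline ARDS status. Baseline cases plus new cases then give the ever-ARDS count, so both readings of the endpoint are covered.

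Keep the by-visit table as supportive and state its denominator. Worsening from baseline severity could be added, but it is not part of the stated endpoint.

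The cost is one extra table and no new data. There are two downsides. The at-risk group is smaller: 40, 25, 15 or 10 per arm if 20%, 50%, 70% or 80% have ARDS on Day 1 (assumed range). And ARDS that starts and resolves between assessments is missed, so the count is of ARDS observed at scheduled assessments and should be labelled that way.

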### **Assessment of SOFA score**

The SOFA score will be assessed on Days 1, 5, 15, and 29. Change from baseline in SOFA score to Days 5, 15, and 29 will be summarized for each treatment group by visit.

Mean change in SOFA scores through Day 29 will be evaluated by fitting a linear mixed-effects model for repeated measures (MMRM). The model will include change from baseline in SOFA score as the repeated dependent variable; treatment (as a class variable), visit (as a class variable including Days 5, 15, and 29), and treatment-by-visit interaction as fixed effects; baseline SOFA

score, age and gender as covariates; and measures within subject at each visit as a repeated measure. An unstructured covariance matrix will be used to model the within-subject error. If the fit of the unstructured covariance structure fails to converge, a compound symmetry covariance structure will be used. Parameters will be estimated using restricted maximum likelihood with the Kenward-Roger method for calculating the denominator degrees of freedom. Missing data will not be imputed. From this model, the least-squares (LS) means and 95% CIs for each treatment group, the treatment difference in the LS means, the 95% CI for the difference, and the associated p-value will be reported on Days 5, 15 and 29, as well as for the average across all post-baseline visits.

### **Assessment of clinical severity**

The NEWS will be calculated based on 7 clinical parameters and recorded on the eCRF. The absolute value and change from baseline in the total score from Day 1 through Day 29 will be summarized by treatment group and visit using descriptive statistics.

Change in NEWS total score through Day 29 will be evaluated by fitting a linear MMRM. The model will include change from baseline in NEWS total score as the repeated dependent variable; treatment (as a class variable), visit (as a class variable), and treatment-by-visit interaction as fixed effects; baseline NEWS total score, age and gender as covariates; and measures within subject at each visit as a repeated measure. An unstructured covariance matrix will be used to model the within-subject error. If the fit of the unstructured covariance structure fails to converge, a compound symmetry covariance structure will be used. Parameters will be estimated using restricted maximum likelihood with the Kenward-Roger method for calculating the denominator degrees of freedom. Data collected starting at the Day 2 visit and up to the Day 29 visit will be included in this analysis. Missing data will not be imputed. From this model, the least-squares (LS) means and 95% CIs for each treatment group, the treatment difference in the LS means, the 95% CI for the difference, and the associated p-value will be reported on Days 15 and 29, as well as for the average across all post-baseline visits.

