### **Ordinal scales**

- a) The absolute value and change from baseline in the Ordinal scale from Day 1 through Day

29 will be summarized by treatment group and visit using descriptive statistics.

Mean change in Ordinal scales through Day 29 will be evaluated by fitting a linear mixed-effects model for repeated measures (MMRM). The model will include change from baseline in Ordinal scale as the repeated dependent variable; treatment (as a class variable), visit (as a class variable), and treatment-by-visit interaction as fixed effects; baseline Ordinal scale, age and gender as covariates; and measures within subject at each visit as a repeated measure. An unstructured covariance matrix will be used to model the within-subject error. If the fit of the unstructured covariance structure fails to converge, a compound symmetry covariance structure will be used. Parameters will be estimated using restricted maximum likelihood with the Kenward-Roger method for calculating the denominator degrees of freedom. Data collected starting at the Day 2 visit and up to the Day 29 visit will be included in this analysis. Missing data will not be imputed. From this model, the least-squares (LS) means and 95% CIs for each treatment group, the treatment difference in the LS means, the 95% CI for the difference, and the associated p-value will be reported on Days 15 and 29, as well as for the average across all post-baseline visits.

- b) The proportion of subjects in each severity category of the 7-point Ordinal scale at Day 15 and Day 29 will be tabulated. The difference in severity category distribution between treatment groups at Day 15 and Day 29 will be examined using proportional-odds cumulative logit model. The cumulative logits model will compare lower ordinal scales to higher ones, or equivalently, less favorable outcomes to more favorable ones. The model may be adjusted for baseline characteristics such as age and gender, if appropriate. The estimated odds ratio and 95% CI will be presented. Graphical illustrations of the fitted model will also be presented for Day 15 and Day 29.

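### The SOFA, NEWS and Ordinal MMRMs use one baseline slope for all visits; a baseline-by-visit term could recover a modest amount of precision at the reported visits, most cleanly for SOFA

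*SAP*

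**What the plan says.** All three models are in SAP section 6.2.

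- **NEWS** (Assessment of clinical severity): the fixed effects are "treatment (as a class variable), visit (as a class variable), and treatment-by-visit interaction as fixed effects", with "baseline NEWS total score, age and gender as covariates". On timing: "Data collected starting at the Day 2 visit and up to the Day 29 visit will be included in this analysis". On covariance: "An unstructured covariance matrix will be used to model the within-subject error". Compound symmetry is the fallback if that fit does not converge.
- **SOFA** (Assessment of SOFA score): "treatment (as a class variable), visit (as a class variable including Days 5, 15, and 29), and treatment-by-visit interaction as fixed effects", with baseline SOFA, age and gender as covariates and the same covariance rule.
- **Ordinal scale** (Ordinal scales): "baseline Ordinal scale, age and gender as covariates; and measures within subject at each visit as a repeated measure", with the same visits and covariance rule as NEWS.

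None of the three contains a baseline-by-visit term. Treatment differences are reported at Days 15 and 29 (also Day 5 for SOFA) and averaged over post-baseline visits. SAP sections 4.5 and 9 describe an exploratory trial of about 100 subjects, with no multiplicity adjustment and no power calculation.

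**The concern.** The slope of a change score on its baseline is (correlation with baseline x SD ratio) minus 1. With stable spread it is near 0 one day after baseline and moves towards -1 as the correlation fades. A main-effect-only model replaces these different slopes with one value. Under unstructured covariance that value is drawn towards early visits, where residual variance given baseline is smallest, while most of the reported contrasts are at late visits.

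At stake is efficiency. Where the common slope differs from the slope at a visit, that contrast has a larger standard error than the recorded baseline allows, and part of any chance baseline difference stays in it. Entry runs from supplemental oxygen to mechanical ventilation (Protocol 5.1), and no stratification factor is described (Protocol 4.3.2, SAP 3.2.1), so some chance imbalance in severity is possible.

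**Working it through.** The documents give no effect size, SD, correlation or power for these scores, so there is no planned figure to reproduce. Everything below uses assumed values, 50 per arm, large-sample formulas and complete data unless stated.

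**Formulas** (baseline SD = 1)
- True change slope at visit t: g_t = r_t x SD ratio - 1. Residual variance: S_tt = SD_t^2 x (1 - r_t^2).
- Fitted common slope: b = 1'S^-1 g / 1'S^-1 1 (unstructured), or the plain mean of the g_t (compound symmetry, complete data).
- SE inflation against visit-specific slopes: sqrt(1 + (g_t - b)^2 / S_tt).
- Imbalance left in the estimate: |g_t - b| x baseline difference. One SE of that difference is sqrt(2/50) = 0.2 SD.

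**SOFA, Day 29, unstructured, equal SDs** (post-baseline correlations set to ratios of the baseline correlations)
- Correlations with baseline 0.7/0.45/0.25: g = -0.75, b = -0.443, S = 0.9375. Variance ratio 1 + 0.307^2/0.9375 = 1.10; SE +5%.
- Correlations 0.8/0.4/0.2: g = -0.80, b = -0.355, S = 0.96. Ratio 1 + 0.445^2/0.96 = 1.21; SE +10%.
- Moderate decay, 0.77/0.54/0.36: about +5%, and about +1% at Day 15.
- SD doubling or tripling by Day 29: at most +0.3%. Constant correlation and SD: 0%.
- A 0.2 SD baseline difference leaves 0.06 SD (first case) or 0.09 SD (second case).

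**NEWS, Day 29, 28 daily visits, equal SDs**

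| Assumption | Covariance | g | b | SE inflation | Left from 0.2 SD |
|---|---|---|---|---|---|
| Daily correlation 0.92, no visit-level noise | Unstructured | -0.903 | -0.216 | 21% | 0.14 |
| Same, 15% of variance is visit-level noise | Unstructured | -0.918 | -0.461 | 10% | 0.09 |
| Same, 30% noise | Unstructured | -0.932 | -0.614 | 5% | 0.06 |
| Daily correlation 0.92, no noise | Compound symmetry | -0.903 | -0.629 | 4% | 0.05 |

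First row: 0.92^28 = 0.097, so S = 0.991 and sqrt(1 + 0.687^2/0.991) = 1.21. At Day 15 the four rows give +12%, +4%, +1.5% and about 0%. With slower decay (0.95 per day) and 10% noise, Day 29 is +12%. A constant slope again gives 0%.

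**Ordinal scale.** Inclusion criterion 3b requires ventilation and/or oxygen, so baseline falls in categories 2 to 4, while Day 29 can span 1 to 7. With Day 29 SD 2.5 times baseline, daily correlation 0.92 and unstructured covariance: g = 0.097 x 2.5 - 1 = -0.758, b = -0.054, S = 6.19. This gives sqrt(1 + 0.704^2/6.19) = 1.04, or +4% (Day 15: +3%).

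**What this means for power.** With 50 per arm, a 0.56 SD effect has z = 0.56/0.2 = 2.80 and 80% power. SE +5% gives Phi(2.80/1.05 - 1.96) = 76%; SE +10% gives 72%.

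**Parameter counts.** Unstructured covariance: 28 x 29/2 = 406 (NEWS, Ordinal) and 3 x 4/2 = 6 (SOFA). Baseline-by-visit adds 27 and 2.

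**The case against.** The strongest reply is that the plan contains no error. Baseline is already a covariate in all three models, the test is valid, and the treatment contrast is unbiased over randomization. This stands: the choice is between two valid specifications.

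A reader might infer that baseline is certainly under-adjusted at Days 15 and 29, that the estimates are biased, and that the Day 29 standard error is inflated by about 21% (power about 61% instead of 78% for a 0.55 SD effect). The documents do not support that reading.

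- They give no correlations or SDs. If spread widens, the gap shrinks, and with SD tripling the change slope can change sign. What remains after a chance imbalance is conditional on that imbalance; it is not systematic bias.
- The 21% needs pure daily decay, no visit-level noise, constant SD and a converged 28-visit unstructured fit. Constant SD does not suit the Ordinal scale, given its restricted entry range.
- A 406-parameter matrix from about 100 subjects may well not converge, and the planned fallback then brings the same scenario down to about 4%.

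The fallback argument has limits. It hardly applies to SOFA, with only six covariance parameters; if SOFA did fall back, the loss could move to Day 5 (SE +5% to +14% in the two SOFA correlation cases above). The 4% also assumes complete data. Discharged subjects are seen only at Days 15 and 29 after Day 10, which gives early visits more weight. If discharge is unrelated to the score, with an assumed median 10 to 20 days after Day 3, the Day 29 figure becomes 6-8%. Discharge or death related to the score was not modelled.

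**Conclusion.** The concern holds as a conditional, modest loss of precision. The omission is plain in the text; its cost is zero if the baseline slope is constant and grows as the association fades with stable spread. Under the stated assumptions, the Day 29 SE inflation is:

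- **SOFA:** about 0-10%, with about 5% under moderate decay and equal SDs.
- **NEWS:** about 0-10% under unstructured covariance (12% in one setting), near 20% only in the extreme case, and at most about 4% under the fallback with complete data.
- **Ordinal scale:** at most about 4% if its Day 29 SD is 2.5 times baseline.

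Severity is low. Only secondary endpoints of an exploratory trial are affected. The mortality analysis is untouched, and the Ordinal scale also has separate proportional-odds analyses at Days 15 and 29 that do not use the common slope. The case is clearest for SOFA.

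**What to change.** In SAP 6.2, add baseline SOFA x visit as a fixed effect in the SOFA MMRM, and estimate the Day 5, 15, 29 and average contrasts at the overall mean baseline. Do the same for NEWS and the Ordinal scale where the model converges, and state in advance that the term is dropped if it does not.

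The cost is one line of SAP text and code per model, with no new data. SOFA gains 2 parameters. NEWS and Ordinal gain up to 27 each, on top of up to 406 covariance parameters and with days on which only inpatients contribute, so convergence may suffer there. If the sponsor wants the smallest change, SOFA alone is enough to justify it.
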